### 10.3 Disease Parameters

10.3.1 Measurable disease. Measurable disease is the presence of at least one (1) lesion that can be accurately measured in at least one dimension with longest diameter  $\geq 20$  millimeters (mm) using conventional techniques (CT, MRI, x-ray) or  $\geq 10$  mm with spiral CT scan. Measurable lesions must be at least 2 times the slice thickness in mm. All tumor measurements must be recorded in millimeters (or decimal fractions of centimeters).

10.3.2 Target lesions: The primary tumor is the target lesion.

### 10.4 Methods for Evaluation of Measurable Disease

All measurements should be taken and recorded in metric notation, using a ruler, calipers, or digital measurement tool. All baseline evaluations should be performed as closely as possible to the beginning of treatment and never more than 4 weeks before the beginning of the treatment.

The same method of assessment and the same technique should be used to characterize each identified and reported lesion at baseline and during follow-up. Imaging-based evaluation is preferred to evaluation by clinical examination when both methods have been used to assess the anti-tumor effect of a treatment.

10.4.1 Clinical lesions. Clinical lesions will only be considered measurable when they are superficial (e.g., skin nodules and palpable lymph nodes). For the case of skin lesions, documentation by color photography, including a ruler to estimate the size of the lesion, is recommended.

10.4.2 Conventional CT and MRI. These techniques should be performed with cuts of 10 mm or less in slice thickness contiguously. Spiral CT should be performed using a 5 mm contiguous reconstruction algorithm. This applies to tumors of the chest, abdomen, and

pelvis. Head and neck tumors and those of extremities usually require specific protocols.

10.4.3 Endoscopy, Laparoscopy. The utilization of these techniques for objective tumor evaluation has not yet been fully and widely validated. Their uses in this specific context require sophisticated equipment and a high level of expertise that may only be available in some centers. Therefore, the utilization of such techniques for objective tumor response should be restricted to validation purposes in reference centers. However, such techniques may be useful to confirm complete pathological response when biopsies are obtained.

10.4.4 Cytology, Histology. These techniques can be used to differentiate between partial responses (PR) and complete responses (CR) in rare cases (e.g., residual lesions in tumor types, such as germ cell tumors, where known residual benign tumors can remain). The cytological confirmation of the neoplastic origin of any effusion that appears or worsens during treatment when the measurable tumor has met criteria for response or stable disease is mandatory to differentiate between response or stable disease (an effusion may be a side effect of the treatment) and progressive disease.

## 10.5 Response Criteria

### 10.5.1 Evaluation of Target Lesions

10.5.1.1 Complete Response (CR): Disappearance of all target lesion.

10.5.1.2 Partial Response (PR): At least a 30% decrease in the sum of the longest diameter (LD) of target lesion, taking as reference the baseline sum LD.

10.5.1.3 Progressive Disease (PD): At least a 20% increase in the sum of the longest diameter (LD) of target lesion, taking as reference the smallest sum LD recorded since the treatment started or the appearance of one or more new lesions (new lesions must be > slice thickness).

10.5.1.4 Stable Disease (SD): Neither sufficient shrinkage to qualify for PR nor sufficient increase to qualify for PD, taking as reference the smallest sum LD since the treatment started.

10.5.1.5 Unknown (UN): Assessment of target lesions cannot be made due to insufficient or unevaluable data. In this case, a concise explanation must be given.

**Note:** If tumor response data is missing for target lesions, the overall assessment must be UN unless there is new disease that would result in an overall assessment of PD. However, if there is missing or unevaluable data for non-target lesions, but data is available for all target lesions, the overall response for that time point will be assigned based on the sum LD of all target lesions. Additionally, the assessment of CR cannot be made if there is missing or unevaluable data for non-target lesions. In this case, the overall assessment would be PR.

## 10.6 Duration of Response

10.6.1 Duration of overall response: The duration of overall response is measured from the time measurement criteria are met for CR or PR (whichever is first recorded) until the first date that recurrence or PD is objectively documented, taking as reference for PD the smallest measurements recorded since the treatment started.

10.6.2 Duration of overall complete response: The duration of overall CR is measured from the time measurement criteria are first met for CR until the first date that recurrent disease is objectively documented.

10.6.3 Duration of stable disease: Stable disease is measured from the start of the treatment until the criteria for progression are met, taking as reference the smallest measurements recorded since the treatment started.

## 11 ADVERSE EVENT REPORTING REQUIREMENTS

### 11.1 Definitions

11.1.1 Adverse Event (AE)

An adverse event (AE) is any undesirable sign, symptom or medical condition or experience that develops or worsens in severity after starting the first dose of study treatment or any procedure specified in the protocol, even if the event is not considered to be related to the study.

Abnormal laboratory values or diagnostic test results constitute adverse events only if they induce clinical signs or symptoms or require treatment or further diagnostic tests.

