### **1.3 Secondary Objectives**

- 1.3.1 To determine the progression-free survival of patients with locally advanced disease who receive FOLFIRINOX-Losartan and radiation therapy.
- 1.3.2 To determine overall survival in patients treated with FOLFIRINOX-Losartan and radiation therapy.
- 1.3.3 To determine the overall survival of patients with locally advanced disease who receive FOLFIRINOX-Losartan without radiation (i.e. patients who demonstrate progression at restaging.)
- 1.3.4 To determine the toxicity of FOLFIRINOX – Losartan in patients with locally advanced pancreatic cancer.
- 1.3.5 To determine the toxicity of FOLFIRINOX – Losartan and radiation in patients with locally advanced pancreatic cancer.

- 1.3.6 To determine the rate of downstaging to surgical resection of FOLFIRINOX-Losartan followed by radiation in patients with locally advanced pancreatic cancer.
- 1.3.7 To determine the correlation between a panel of somatic genetic mutations (SNaPSHOT) and outcome in locally advanced pancreatic cancer treated with FOLFIRINOX-Losartan +/- radiation/capecitabine.
- 1.3.8 To determine the correlation between circulating biomarkers of TGF- $\beta$ 1 downregulation, including circulating Collagen I levels, and outcome in locally advanced pancreatic cancer treated with FOLFIRINOX-Losartan +/- radiation/capecitabine.
- 1.3.9 To describe quality of life, symptom burden and mood in the study population.
- 1.3.10 To measure utilization of health services (emergency room, hospital and intensive care unit, palliative care) in the study population.

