## **6 EXPECTED TOXICITIES AND DOSING DELAYS/MODIFICATIONS**

Dose delays and modifications will be made using the following recommendations. Toxicity assessments will be done using the NCI Common Terminology Criteria for Adverse Events (CTCAE v4.0) which is identified and located on the CTEP website at:

<http://ctep.cancer.gov/reporting//ctc.html>).

If possible, symptoms should be managed symptomatically. In the case of toxicity, appropriate medical treatment should be used (including anti-emetics, anti-diarrheals, etc.).

All adverse events experienced by participants will be collected from the time of the first dose of study treatment, through the study and until the final study visit. Participants continuing to experience toxicity at the off study visit may be contacted for additional assessments until the toxicity has resolved or is deemed irreversible.

Grade 3 or 4 toxicities that are due to biliary ductal dilatation and resolved with placement of a biliary stent or with biliary stent change will not require a dose reduction of FOLFIRINOX, capecitabine, proton radiation therapy or Losartan after stent placement. Therapy may be withheld for procedures like repeat ERCP, and restarted at the treating physician's discretion per standard of care.

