For the purposes of this study, the following grade 4 toxicities are expected in the setting of dehydration, diarrhea or reduced oral intake and will not require expedited serious adverse event reporting: low magnesium, low potassium, and low phosphorus. The following grade 4 toxicities are expected and will not require expedited serious adverse event reporting: low white blood cell count, and neutropenia.

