### 11.2 Procedures for AE and SAE Recording and Reporting

Reporting Participating investigators will assess the occurrence of AEs and SAEs at all participant evaluation time points during the study.

All AEs and SAEs whether reported by the participant, discovered during questioning, directly observed, or detected by physical examination, laboratory test or other means, will be recorded in the participant's medical record and on the appropriate study-specific case report forms.

Except as described in Section 4.2.1.5, the descriptions and grading scales found in the CTEP Active Version of the NCI Common Terminology Criteria for Adverse Events (CTCAE) will be utilized for AE reporting. The CTEP Active Version of the CTCAE is identified and located on the CTEP website at:

[http://ctep.cancer.gov/protocolDevelopment/electronic\\_applications/ctc.htm](http://ctep.cancer.gov/protocolDevelopment/electronic_applications/ctc.htm).

All appropriate treatment areas should have access to a copy of the CTEP Active Version of CTCAE.

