### 14.3 Analysis of Secondary Endpoints

- 14.3.1 **Progression-free survival:** All patients who start induction chemotherapy will be analyzed based on the definition in Section 10.1.2. The progression-free survival duration of patients who are alive and progression will be censored at their date of last follow-up. The Kaplan-Meier method will be used to estimate progression-free survival with 90% confidence intervals constructed by Greenwood's formula.
- 14.3.2 **Overall survival:** Overall survival will be defined as the duration between the start date of protocol therapy and death. The survival time of patients who are not known to have died will be censored at the date they are last known to be alive. The Kaplan-Meier method will be used to estimate overall survival estimation with 90% confidence intervals constructed by Greenwood's formula.
- 14.3.3 **Toxicities:** All patients who begin induction chemotherapy will be included in the toxicity profile of Losartan combined with induction FOLFIRINOX. Summaries of toxicities will include the frequency and proportion of patients experiencing each toxicity, as well as summaries by toxicity category and toxicity grade. We shall report separately the additional treatment-related toxicity following radiation in patients who do not have progressive disease at the restaging interval after induction chemotherapy.
- 14.3.4 **Downstaging:** A fraction of patients may proceed to surgical resection following the conclusion of protocol therapy if the tumor shrinkage were sufficient to be considered resectable. The rate of downstaging to surgical resection will be determined as the proportion of initially unresectable patients who eventually undergo pancreaticoduodenectomy or distal pancreatectomy. The pathologic downstaging rate will be calculated as the proportion of resected patients with the primary tumor and nodes downstaged based on final pathology of the surgical specimen.
- 14.3.5 **Correlation of biomarkers with outcome:** Correlative studies will be conducted to characterize circulating collagen and angiogenesis biomarkers (8.1.1), as well as somatic genetic mutations characterized by the SNaPshot platform (8.1.2). Due to the modest patient numbers, analysis will be limited generally to two-group comparisons of each

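### The adverse event definition filters out asymptomatic laboratory abnormalities ahead of the toxicity tables, so all-grade rates of anemia, raised ALT and mild cytopenia can be under-counted

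*Combined protocol and SAP*

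**What the plan says.** Objective 1.3.4 reads "To determine the toxicity of FOLFIRINOX" with losartan; objective 1.3.5 asks the same once radiation is added. Section 14.3.3 answers both descriptively. "All patients who begin induction chemotherapy will be included in the toxicity profile of Losartan combined with induction FOLFIRINOX", and "Summaries of toxicities will include the frequency and proportion of patients experiencing each toxicity", with further summaries by category and grade and a separate report of toxicity after radiation. It does not name the data source.

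Section 11.1.1 limits what can be recorded: abnormal laboratory results "constitute adverse events only if they induce clinical signs or symptoms or require treatment or further diagnostic tests". Section 11.2 says that events "detected by physical examination, laboratory test or other means, will be recorded", but only findings that are adverse events under 11.1.1 come within that rule. Section 11.4.2 sends non-serious adverse events to the toxicity case report forms, and the schedule in 12.1.2 lists a single Toxicity/Adverse Event Report Form. Laboratory values go on a separate Lab Form.

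On grading, section 6 fixes CTCAE v4.0 for toxicity assessment. Section 11.2 says the "CTEP Active Version of the NCI Common Terminology Criteria for Adverse Events (CTCAE) will be utilized for AE reporting", with an exception for Section 4.2.1.5. Section 4 has only 4.1 and 4.2.

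**The concern.** Elsewhere the protocol treats laboratory values as toxicities in their own right, whether or not the patient feels anything. The tables in 6.1.1 list neutropenia, anemia, thrombocytopenia and ALT as adverse events at all grades. Section 11.1.2 says: "The following grade 4 toxicities are expected and will not require expedited serious adverse event reporting: low white blood cell count, and neutropenia". The hematologic table in 6.2.2.1 changes the oxaliplatin dose permanently for grade 1 thrombocytopenia, with no hold, treatment or extra test, so an event that alters treatment for the rest of the course need not be an adverse event under 11.1.1.

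If the combined form is the source for 14.3.3, the filter can only remove laboratory events. The toxicity profile would then look milder than the graded values, in a trial with no control arm to show the shortfall. The phrase about further diagnostic tests is also undefined. Whether a repeat or already scheduled blood count satisfies it is left to each investigator, so recording may be uneven as well as low.

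The two statements on the CTCAE version add a separate problem. Accrual is projected over 4.5 years (14.2). If the active version changes in that time, one table could mix grades from two versions.

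**Working it through.** **The plan's own figure.** The plan computes nothing for toxicity. Its one computed design figure, at least 9 R0 resections in 50 patients, reproduces by exact binomial: type 1 error 0.0579 at 10% (stated 6%) and power 0.9084 at 25% (stated 91%). Nothing here touches it.

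**Step 1: which values meet 11.1.1 through the protocol's own rules.**

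| Finding | Protocol action | Meets 11.1.1 without symptoms? |
|---|---|---|
| Day 1 neutropenia, grade 3-4 | Hold until recovery; supportive care and antibiotics (6.2.2.1) | Ordinarily yes |
| Day 1 neutropenia or thrombocytopenia, grade 2 | Hold until recovery, which needs a repeat count (6.2.2.1) | Ordinarily yes |
| Day 1 thrombocytopenia, grade 3-4 | Hold until recovery, which needs a repeat count (6.2.2.1) | Ordinarily yes |
| Potassium 5.0 mmol/L or more | Check for hemolysis, hold losartan, recheck in one week (Hyperkalemia, under 6.2) | Yes |
| Thrombocytopenia, grade 1 | Permanent oxaliplatin reduction; no retest required (6.2.2.1) | Not by rule |
| Neutropenia, grade 1 | No row in the table | Not by rule |
| Anemia; ALT | No row in the tables of 6.2 | Not by rule |
| Nadir on the weekly cycle 1 draw that recovers by the next Day 1 | Depends on any treatment or extra test | Not if neither is needed |

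The last four rows are exposed.

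**Step 2: how many patients could be affected.** Inputs are the all-grade (A) and grade 3/4 (G) percentages in 6.1.1.1 and 6.1.1.2 and the accrual goal of 50 (14.2). The part below grade 3 is A − G; in patients it is 50 × (A − G)/100. If a fraction f of those events fails 11.1.1, the recorded all-grade rate is A − f × (A − G). The documents give no value for f, so it is run over its whole range.

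| Toxicity | A | G | A − G | Patients of 50 | Recorded rate, f = 0 / 0.5 / 1 |
|---|---|---|---|---|---|
| Anemia | 90.4 | 7.8 | 82.6 | 41.3 | 90.4 / 49.1 / 7.8% |
| Thrombocytopenia | 75.2 | 9.1 | 66.1 | 33.1 | 75.2 / 42.1 / 9.1% |
| ALT | 64.8 | 7.3 | 57.5 | 28.8 | 64.8 / 36.0 / 7.3% |
| Neutropenia | 79.9 | 45.7 | 34.2 | 17.1 | 79.9 / 62.8 / 45.7% |

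**Step 3: why these are ceilings.** The thrombocytopenia count includes grade 2, which Step 1 mostly retains. The neutropenia row is the weakest: 79.9% sits in the all-grades column of 6.1.1.1, but 6.2.2.1 calls the same figure grade 2-4. On that second reading the 17 patients are all grade 2 and mostly retained on Day 1. This trial also plans prophylactic pegfilgrastim, while 42.5% of the reference FOLFIRINOX arm needed G-CSF (2.2.2), so the neutropenia rate may not carry over. Anemia and ALT have no such protection.

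**The case against.** The strongest reply is that 14.3.3 speaks of toxicities, not adverse events. Section 6 grades toxicity by CTCAE, 11.1.2 calls grade 4 neutropenia a toxicity, and the values are on the Lab Form. On this reading 11.1.1 never reaches the tables. Part of this stands: under-counting is possible, not certain. But the plan's only toxicity form is the combined one, adverse events are routed to it, and no sentence directs grading from the Lab Form.

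Three stronger readings are tempting, and the documents do not support them.

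- **Severe neutropenia nearly vanishes.** Setting grade 3/4 neutropenia (50 × 0.457 = 22.9 patients) against febrile neutropenia (50 × 0.072 = 3.6) suggests that about 4 patients would be counted where 23 belong. That treats only symptomatic cases as recorded and ignores treatment and further tests, the other two routes into the definition. A Day 1 ANC of 900 or platelet count of 70K leads to a hold with repeat counts, and the ANC also to supportive care. Both ordinarily qualify.
- **Losartan's potassium signal is lost.** The mandatory recheck makes a potassium of 5.0 mmol/L or more an adverse event.
- **A planned comparison is biased.** No comparison with the 6.1.1 tables is planned; 6.1 offers its lists for dose modification and expedited reporting. Readers may still compare, and the all-grade column would then be the unsafe one.

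On grading, the documents do not show that the active CTCAE version changed during accrual, so mixed versions are a risk, not a finding.

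**Conclusion.** The point holds in limited form. Section 11.1.1, acting through the combined form, can lower the counts behind objectives 1.3.4 and 1.3.5. The exposed items are asymptomatic anemia and ALT elevation, grade 1 thrombocytopenia, grade 1 neutropenia, and nadirs that recover without treatment or a repeat test. The effect falls mainly on all-grade rates. Grade 3/4 rates move only where a severe value prompts neither treatment nor a further test.

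The ceilings are about 41, 33, 29 and 17 of 50 patients for anemia, thrombocytopenia, ALT and neutropenia. They assume that the 6.1.1 rates apply here. The loss within them is unknown and could be nil if the sponsor already grades from the Lab Form. The direction is certain: the filter cannot raise a count.

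The CTCAE version conflict between sections 6 and 11.2 is a plain contradiction. Its effect cannot be sized from the documents.

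**What to change.** - **14.3.3:** state that laboratory toxicities are graded by CTCAE v4.0 from all protocol-scheduled Lab Form values, regardless of symptoms, and reported as worst grade per patient, separately for induction and radiation. State that the 11.1.1 limit applies to adverse event reporting only. Showing the baseline grade alongside would help, since 3.1.8 admits patients with raised AST or ALT and sets no hemoglobin limit.
- **11.2:** replace the reference to the active version with CTCAE v4.0, to match section 6.
- **11.2 exception:** correct the reference to Section 4.2.1.5; do not delete it. It appears to be meant for the protocol's own oxaliplatin sensory neuropathy scale in 6.2, which the sponsor should confirm. Deletion would leave 11.2 in conflict with that scale.

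The cost is wording and some programming. Lab Form values are already due for each scheduled assessment, so the rule can cover the first 32 patients as well as the remaining 18. Reported laboratory toxicity rates will be higher. One limit remains: after cycle 1 the calendar schedules blood counts every other week, so mid-cycle nadirs in later cycles may go unseen under either approach. Sample size, type 1 error and power are unchanged.

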#### 11.1.2 Serious adverse event (SAE)

A serious adverse event (SAE) is any adverse event, occurring at any dose and regardless of causality that:

- Results in death
- Is life-threatening. Life-threatening means that the person was at immediate risk of death from the reaction as it occurred, i.e., it does not include a reaction which hypothetically might have caused death had it occurred in a more severe form.
- Requires or prolongs inpatient hospitalization (i.e., the event required at least a 24-hour hospitalization or prolonged a hospitalization beyond the expected length of stay). Hospitalization admissions and/or surgical operations scheduled to occur during the study period, but planned prior to study entry are not considered SAEs if the illness or disease existed before the person was enrolled in the trial, provided that it did not deteriorate in an unexpected manner during the trial (e.g., surgery performed earlier than planned).
- Results in persistent or significant disability/incapacity. Disability is defined as a substantial disruption of a person's ability to conduct normal life functions.
- Is a congenital anomaly or birth defect; or
- Is an important medical event when, based upon appropriate medical judgment, it may jeopardize the participant and require medical or surgical intervention to prevent one of the outcomes listed above. Examples of

such medical events include allergic bronchospasm requiring intensive treatment in an emergency room or at home; blood dyscrasias or convulsions that do not result in inpatient hospitalization, or the development of drug dependency or drug abuse.

Events **not** considered to be serious adverse events are hospitalizations for:

- routine treatment or monitoring of the studied indication, not associated with any deterioration in condition, or for elective procedures
- elective or pre-planned treatment for a pre-existing condition that did not worsen
- emergency outpatient treatment for an event not fulfilling the serious criteria outlined above and not resulting in inpatient admission

respite care

For the purposes of this study, the following grade 4 toxicities are expected in the setting of dehydration, diarrhea or reduced oral intake and will not require expedited serious adverse event reporting: low magnesium, low potassium, and low phosphorus. The following grade 4 toxicities are expected and will not require expedited serious adverse event reporting: low white blood cell count, and neutropenia.

